## 6. BIAS

### 6.1 Methods to minimize bias

#### 6.1.1 Patient enrolment

This is a single arm, open label study; no randomization or blinding will be performed.

Investigators should keep a record (ie, the patient screening log) of patients who entered screening.

At screening/baseline (Days -28 to -1), the Investigators or suitably trained delegate will:

- Obtain signed informed consent before any study specific procedures are performed. If laboratory or imaging procedures were performed for alternate reasons prior to signing consent, these can be used for screening purposes with consent of the patient. However, all screening laboratory and imaging results must have been obtained within 28 days of inclusion.
- Obtain a unique enrolment number (E-code), through the Interactive Web Response System (IWRS). This number is the patient's unique identifier and is used to identify the patient on the electronic case report forms (eCRFs).
- Determine patient eligibility based on inclusion/exclusion criteria. If the patient is ineligible and not included, the IWRS should be contacted to terminate the patient in the system.

Patients will start treatment on Day 1. Treatment should start no more than 3 working days after being included. Patients must not be included and treated unless all eligibility criteria have been met.

If a patient withdraws from participation in the study, then his or her enrolment code cannot be reused.

#### 6.1.2 Procedures for handling incorrectly enrolled patients

Patients who fail to meet the eligibility criteria should not, under any circumstances, be enrolled or receive study medication. There can be no exceptions to this rule. Patients who are enrolled, but subsequently found not to meet all the eligibility criteria must not be initiated on treatment, and must be withdrawn from the study.

Where a patient does not meet all the eligibility criteria but is included in error, or incorrectly started on treatment, the Investigator should inform the Study Medical Monitor immediately, and a discussion should occur between the Study Medical Monitor and the Investigator regarding whether to continue or discontinue the patient from treatment. The Study Medical Monitor must ensure all decisions are appropriately documented and that the potential benefit: risk profile remains positive for the patient.

## **6.2 Handling of missing data**

Missing values will not be considered for calculating percentages or any other descriptives, meaning that only valid values will be presented. The number of missing data will be provided for every analysed variable. No use of any method or imputation of data for the handling of missing data is foreseen.

For the questionnaires EORTC QLQ-C30, EORTC QLQ-LC13 and PRO-CTCAE, for each subscale, if < 50% of the subscale items are missing, then the subscale score will be divided by the number of non missing items and multiplied by the total number of items on the subscales. If at least 50% of the items are missing, then that subscale will be treated as missing. Missing single items are treated as missing. The reason for any missing questionnaire will be identified and recorded. If there is evidence that the missing data are systematic, missing values will be handled to ensure that any possible bias is minimized.

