Changes in score compared with baseline will be evaluated. A minimum clinically meaningful change is defined as an absolute change in the score from baseline of ≥ 10 points for scales/items from the EORTC QLQ-C30 (Osoba et al 1998). For example, a clinically meaningful improvement in physical function (as assessed by EORTC QLQ-C30) is defined as an increase in the score from baseline of ≥ 10 points, whereas a clinically meaningful deterioration is defined as a decrease in the score from baseline of ≥ 10 points. At each post-baseline assessment, the change in symptoms/functioning from baseline will be categorised as improvement, no change, or deterioration as shown in Table 15.

Table 14. Mean change and visit response in health related quality of life

Score	Change from Baseline (points)	Visit Response
EORTC QLQ-C30 Global quality of life score	$\geq +10$	Improvement
	≤ -10	Deterioration
	Otherwise	No Change
EORTC QLQ-C30 symptom scales/items	$\geq +10$	Improvement
	≤ -10	Deterioration
	Otherwise	No Change
EORTC QLQ-C30 functional scales	$\geq +10$	Improvement
	≤ -10	Deterioration
	Otherwise	No Change

EORTC QLQ-C30 = European Organisation for Research and Treatment of Cancer 30-item core quality of life questionnaire.

For each subscale, if < 50% of the subscale items are missing, then the subscale score will be divided by the number of nonmissing items and multiplied by the total number of items on the subscales (Fairman et al 2014). If at least 50% of the items are missing, then that subscale will be treated as missing. Missing single items are treated as missing. The reason for any missing questionnaire will be identified and recorded. If there is evidence that the missing data are systematic, missing values will be handled to ensure that any possible bias is minimized.

Time to symptom deterioration

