##### Endpoints analyzed:

- Change from baseline in European Organisation for Research and Treatment of Cancer Quality of Life Questionnaire Core 30 items (EORTC QLQ-C30):

This analysis will be performed for the Intention-to-Treat population (ITT). For the following endpoints, change from baseline is defined as the post-treatment value minus the value at baseline. The % change from baseline will be calculated as:

$$(\text{Postbaseline value} - \text{baseline value}) / \text{baseline value} \times 100.$$

The **EORTC QLQ-C30 v3 questionnaire** is included for the purpose of assessing HRQoL and is a well-established measure of HRQoL/health status. It assesses HRQoL/health status through 9 multi-item scales: 5 functional scales (physical, role, cognitive, emotional, and social), 3 symptom scales (fatigue, pain, and nausea and vomiting), and a global health and quality-of-life (QoL) scale. Six single-item symptom measures are also included dyspnea, insomnia, appetite loss, constipation, diarrhea, and financial difficulties. For each of the 15 domains, final scores are transformed such that they range from 0 to 100, where higher scores indicate greater functioning, greater HRQoL, or greater level of symptoms .

The principle for scoring these scales is the same in all cases:

- Estimate the average of the items that contribute to the scale; this is the raw score.
- Use a linear transformation to standardise the raw score, so that scores range from 0 to 100; a higher score represents a higher ("better") level of functioning, or a higher ("worse") level of symptoms.

For all scales, the *RawScore*, *RS*, is the mean of the component items:

$$\text{RawScore} = \text{RS} = (I_1 + I_2 + \dots + I_n)/n$$

Then for **Functional scales**:

$$\text{Score} = \left\{ 1 - \frac{(\text{RS} - 1)}{\text{range}} \right\} \times 100$$

For **Symptom scales/ items** and **Global health status/ QoL**:

$$\text{Score} = \left\{ \frac{(\text{RS} - 1)}{\text{range}} \right\} \times 100$$

The following outcomes will be analysed for this endpoint:

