#### Endpoints analyzed:

- Change from baseline in European Organisation for Research and Treatment of Cancer Quality of Life Questionnaire Core 30 items (EORTC QLQ-C30) and Questionnaire-Lung Cancer 13 (EORTC QLQLC13):

Scores for the QLQ-C30 and QLQ-LC13 questionnaires will be calculated according to published scoring manuals or the developer's guidelines. Raw scores from scales in both questionnaires will be standardized by linear transformation so that they range from 0 to 100. Higher scores for symptom items indicate greater symptom severity, while higher scores for function and global health status/QoL items indicate better function and health status/QoL. For both questionnaires, a clinically meaningful change will be prespecified as an absolute change in score from baseline of  $\geq 10$  points (either deterioration or improvement). For the five key disease-related symptoms (cough, dyspnea, and chest pain [QLQ-LC13], and fatigue and appetite loss [QLQ-C30]), changes at each visit from baseline to disease progression or end of follow-up (whichever came first) will be analyzed using a mixed model for repeated measures (MMRM) to derive an overall adjusted mean change from baseline, reflecting the average treatment effect over visits. The model assumes PROs will be collected at multiple visits per

patient. Visits with >75% missing data will be excluded from the analysis. The MMRM included treatment, age at baseline (<65 vs ≥65 years), sex, smoking history (smoker vs non-smoker) and visit interaction as fixed factors, and baseline score as a covariate; the model further adjusted for baseline score-by-visit interaction.

Summaries of original and change from baseline values of each symptom scale/item, the global HRQoL score, and each functional domain will be reported by visit.

Time to symptom deterioration and time to quality of life / function deterioration (defined in 4.2.2) will be analyzed by product limit methods to provide summaries of the number and percentage of patients experiencing a clinically meaningful deterioration or death, the median time to deterioration together with the corresponding 95% CIs, as well as the Kaplan-Meier plot. An stratified log-rank test adjusted for therapy will be used with HR s and 95% CIs calculated using a stratified Cox proportional hazards model.

Symptom improvement rate and Quality of life / function improvement (defined in 4.2.2) will be summarized.

- Changes from baseline in PRO-CTCAE:

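### The missing-item rule prorates a sum, but the SAP's subscale score is a transformed mean, so several ways of applying it distort incomplete EORTC scales

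*SAP*

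**What the plan says.** SAP 4.2.2.2 sets out the scoring in two steps. First: "Estimate the average of the items that contribute to the scale; this is the raw score". Then: "Use a linear transformation to standardise the raw score, so that scores range from 0 to 100". The printed formula divides the item total by n. It does not say whether n falls when an item is unanswered.

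SAP 6.2 adds the missing-item rule. It applies "if < 50% of the subscale items are missing", and then "the subscale score will be divided by the number of non missing items and multiplied by the total number of items" on the subscale. Otherwise: "If at least 50% of the items are missing, then that subscale will be treated as missing". Protocol 9.5.2.3 has the same instruction ("then the subscale score will be divided by the number of nonmissing items") under QLQ-C30, and carries the approach over to QLQ-LC13.

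Three other statements bear on this:

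- SAP 5.2.2 says that the scores "will be calculated according to published scoring manuals or the developer's guidelines". It names no manual, and the SAP's only reference is the 1993 QLQ-C30 development paper.
- SAP 6.2 says, just before giving the rule, that no method or imputation for missing data is foreseen. SAP 5 says much the same.
- SAP 5.2.2 fixes the yardstick: "a clinically meaningful change will be prespecified as an absolute change in score from baseline of" at least 10 points, for both questionnaires.

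**The concern.** Dividing by the answered items and multiplying by all the items turns a partial sum into an estimated full sum. A mean over the answered items needs no such step, because it is already on the full-scale metric. The SAP defines only a mean and a 0–100 transform of it, so the term 'subscale score' in SAP 6.2 has no sum to refer to. The nearest defined quantity is the 0–100 score.

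A programmer who scores the answered items and then applies SAP 6.2 as written would change the score of a patient whose answers did not change. The possible shifts are large beside the 10-point threshold. They would enter the repeated-measures model for the key symptoms, the change-from-baseline summaries by visit and the protocol's visit-level categories. Two programmers following the same text could also produce different scores.

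**Working it through.** The documents give no figure on this point to reproduce. The check applies the SAP's own formulas to incomplete scales.

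**Inputs**

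- Symptom score = (RS − 1)/range × 100; functional score = {1 − (RS − 1)/range} × 100 (SAP 4.2.2.2). For items coded 1 to 4 the range is 3. Complete data then give exactly 0 to 100.
- Factor k = n/(n − m) for m missing items of n, allowed only if m/n is below 50% (SAP 6.2).
- LC13 breathlessness has three items, questions 33–35 (Protocol Appendix I). Physical functioning is taken as questions 1–5 (Protocol Appendix H). The documents print no item-to-scale map, so three items for fatigue, four for emotional functioning and two for the other C30 multi-item scales are assumptions.

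**Permitted factors**

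- 3 items, 1 missing: 3/2 = 1.50
- 4 items, 1 missing: 4/3 = 1.33
- 5 items, 1 missing: 5/4 = 1.25
- 5 items, 2 missing (40%): 5/3 = 1.67
- 2 items, 1 missing: exactly 50%, so the scale is set to missing and never rescaled

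**Same answers, five readings.** Every answered item is 'a little' (coded 2) and one item is missing.

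| Rule applied to | 3-item symptom scale (correct 33.3) | 5-item functional scale (correct 66.7) |
|---|---|---|
| 0–100 score from the mean of answered items | 33.3 × 1.5 = 50.0 | 66.7 × 1.25 = 83.3 |
| Mean of answered items, then transformed | RS 2 × 1.5 = 3, score 66.7 | RS 2 × 1.25 = 2.5, score 50.0 |
| 0–100 score from answered total over full n | RS 4/3, score 11.1 × 1.5 = 16.7 | RS 8/5, score 80.0 × 1.25 = 100.0 |
| Answered total over full n, then transformed | RS 4/3 × 1.5 = 2, score 33.3 | RS 8/5 × 1.25 = 2, score 66.7 |
| Plain sum, then divided by n | 4/2 × 3 = 6, RS 2, score 33.3 | 8/4 × 5 = 10, RS 2, score 66.7 |

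The last two readings are right and the first three are wrong. The second raises symptom scores but lowers functional ones. The third lowers this symptom score.

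**When the shift reaches 10 points**

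- First reading: the shift is (k − 1) × score, so the correct score must be at least 10/(k − 1). That is 40, 30, 20 and 15 for k = 1.25, 1.33, 1.50 and 1.67. The maximum possible score becomes 100k, or 125 to 167. On a three-item scale 100 becomes 150.
- Second reading: the shift is (k − 1) × RS × 33.3. Even at the lowest RS of 1 it is 11.1, 16.7 and 22.2 points for k = 1.33, 1.50 and 1.67. For k = 1.25 it is 8.3 at RS = 1 and reaches 10 once RS is 1.2.

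**Incomplete baseline.** Take the first reading and the three-item symptom scale, with one item skipped at baseline only and the same answers throughout. Baseline is 50.0 and every later score is 33.3, so every change is 33.3 − 50.0 = −16.7. A change that recurs at each visit confirms itself.

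**After the fix.** Answers 2, 2 and missing give RS = 2 and a score of 33.3, the same as 2, 2, 2. The factor is 1.00 and scores stay within 0–100.

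**The case against.** The strongest reply is that the rule can be read correctly. The formula in SAP 4.2.2.2 divides by n. If n is the fixed number of items and a blank adds nothing, SAP 6.2 returns exactly the mean of the answered items. The SAP also says that scores run from 0 to 100 and follow published manuals, and a score of 150 breaches the first of these. In the protocol the rule is attributed to a durvalumab pharmacokinetics abstract, while the QLQ-C30 scoring manual is the next entry in the reference list, so a citation slip is plausible.

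This shows that a benign intent is likely. It does not settle the text. Neither document says that blanks count as zero or that the rule precedes the transformation, and a general pointer to manuals does not displace a specific instruction.

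Three further objections largely stand:

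- Improvement needs two consecutive assessments and deterioration needs confirmation at the next one. A single skipped item after baseline therefore often creates no event. The gaps are the protocol's rule that an unconfirmed last deterioration counts, and incomplete baselines.
- The scope is narrow. Of the five key symptoms in SAP 5.2.2, only dyspnoea and fatigue are multi-item.
- These are secondary outcomes in a single-arm descriptive study without formal hypotheses.

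SAP 6.2 also names PRO-CTCAE, and a reader might infer that those data would be distorted too. They would not be: SAP 5.2.2 summarises PRO-CTCAE question by question, so there is no subscale to rescale.

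**Conclusion.** The point holds as an internal mismatch: a rule for sums is attached to a score defined as a transformed mean. On three of the five readings examined it gives wrong values. Where it multiplies the 0–100 score or the mean of the answered items, the factor is 1.25 to 1.67. The upper figure rests on physical functioning having five items.

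A reader might infer that the plan inflates every incomplete scale, or that one skipped item makes a patient a deterioration or improvement event. The documents support neither. Two readings give the correct score, the direction varies with the reading and the type of scale, and the confirmation rules stop many isolated artefacts.

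The real exposure is in scales of three or more items: LC13 dyspnoea, physical functioning and, by assumption, fatigue and emotional functioning. It lies mainly in the repeated-measures model, the by-visit change summaries, the visit categories and patients with an incomplete baseline. The documents give no rate of skipped items, so the number of patients affected cannot be estimated. The primary safety endpoints are untouched.

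**What to change.** In SAP 6.2 and Protocol 9.5.2.3, replace the rule with: *If fewer than 50% of a scale's items are missing, the raw score is the mean of the answered items and is then transformed to 0–100; otherwise the scale is missing.*

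Qualify the statements in SAP 6.2 and SAP 5 that no missing-data method is foreseen, so that they except this rule. Correct the protocol's citation for the rule at the same time. Removing PRO-CTCAE from the sentence is tidying only.

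The cost is one sentence in each document plus the small wording changes. No data collection changes. If scoring programs already exist, check which reading they implement.

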## **6.3 Adjustment for multiple comparisons**

Not applicable.

## **7. INTERIM ANALYSES**

Not applicable by study protocol.

Following interim analysis will be performed:

- Sept 2021: Demographic data & Cancer history: sections 4.3.2 and 4.3.3.
- Oct 2021: Treatment administration: Section 4.3.4. and 5.1. (subgroup analysis will not be included).
- Feb 2022: Progression free survival and QoL: Section 5.2.1 Progression free survival and 5.2.2.

